#### 9.1 Outcome Measures

#### 9.1.1 Primary

There are two primary outcomes in this trial as both are of fundamental importance to decisions regarding the future use of MP-MRI in the diagnostic pathway for the prostate cancer:

- Proportion of men who could safely avoid biopsy as determined by specificity and negative predictive values (NPV)
- 2. Proportion of men correctly identified by MP-MRI to have clinically significant prostate cancer as determined by sensitivity and positive predictive values (PPV)

For the primary outcomes we take DEFINITION ONE (A dominant Gleason pattern  $\geq$  4 and/or a cancer core length  $\geq$  6 mm, see section 2.6) as the criteria for clinically significant prostate cancer as assessed by TPM, the most appropriate reference standard.

Alongside these outcomes, the accuracy of TRUS will also be reported in terms of sensitivity, specificity, NPV, and PPV as listed in the section below. In addition, a head-to-head comparison of the sensitivity of MP-MRI versus TRUS guided biopsy (current standard) will be performed amongst men diagnosed with clinically significant prostate cancer according to TPM.

For the primary outcome, a score of 3 or more on MRI will be used to define a potentially clinically significant cancer (see section 6.1 for details). A dominant Gleason pattern  $\geq$  4 and/or a cancer core length  $\geq$  6 mm will be used for clinically significant cancer (see DEFINITION ONE section 2.6) for the biopsies.

#### 9.1.2 Secondary

• The proportion of men who could safely avoid biopsy, given that they do not have DEFINITION TWO (see section 2.6) prostate cancer as assessed by TPM.

- The proportion of men testing positive on MP-MRI out of those with DEFINITION TWO prostate cancer assessed by TPM.
- Performance characteristics of TRUS versus TPM (sensitivity, specificity, NPV, PPV) according to DEFINITIONS ONE and TWO.
- Evaluation of the optimal combination of MP-MRI functional parameters (T2, DW, DCE) to detect or rule-out clinically significant prostate cancer.
- Intra-observer variability in the reporting of MP-MRI.
- Inter-observer variability in the reporting of MP-MRI.
- Evaluation of socio-demographic, clinical, imaging and radiological variables in relation to the detection of clinically significant prostate cancer.
- Patients' health-related quality of life using the EQ-5D instrument.
- Resource use and costs for further economic evaluation (see Section 10 Cost-effectiveness).
- Translational objectives (see section 2.8).

#### 9.2 Sample Size

Power calculations were performed in relation to:

- Precision around the estimates for the accuracy of MP-MRI in terms of the primary outcome of sensitivity, and
- (2) The head-to-head comparison of the MP-MRI versus TRUS

The largest sample size from (1) and (2) was **714** (as detailed in sections 9.2.2 and 9.2.3) and this was taken as the maximum number of men required to have all 3 tests (MP-MRI, TPM and TRUS biopsy) in this study.

#### 9.2.1 Prevalence of clinically significant cancer

For all calculations we have assumed:

- 15% of the study population will have clinically important prostate cancer as detected by the reference standard (TPM) according to DEFINITION ONE (PRIMARY).
- 25% of the study population will have clinically significant prostate cancer as detected by the reference standard (TPM) according to DEFINITION TWO (less stringent definition).

These estimates act as inflation factors for the total number of men required for the study.

#### 9.2.2 Precision around the accuracy measures of MP-MRI

All calculations are based on 90% power and 5% significance (2-sided). Specified estimates of sensitivity and specificity are considered realistic based on current unpublished and published literature.

#### Specificity of MP-MRI

Assuming a specificity of 77%, in order to demonstrate that the lower 95% confidence interval of specificity is at least 70% or greater, we would require 407 cases of negative or clinically insignificant prostate cancer. This is equivalent to a total of 479 men for DEFINITION ONE and 543 men for DEFINITION TWO.

#### Sensitivity of MP-MRI

Assuming a sensitivity of 75%, in order to demonstrate that the lower 95% confidence interval of sensitivity is at least 60% or greater, we would require 97 cases of clinically significant prostate cancer. This is equivalent to a total of **647** men for DEFINITION ONE and **388** men for DEFINITION TWO.

Since the number of men without clinically significant prostate cancer will be much higher than the number with, the precision for estimating specificity and NPV is much greater.

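### The 97 cases and 407 non-cases in section 9.2.2 match a formula with null and alternative exchanged; the ordinary order gives 103 and 422, and 714 men still cover both

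*Protocol*

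**What the plan says.** Section 9.2.2 opens with the error rates: "All calculations are based on 90% power and 5% significance (2-sided").

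For sensitivity, with an assumed true value of 75%, the protocol says that, to show "the lower 95% confidence interval of sensitivity is at least 60% or greater, we would require 97 cases of clinically significant prostate cancer". It converts this count to 647 "men for DEFINITION ONE and 388 men for DEFINITION TWO".

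For specificity the aim is: "Assuming a specificity of 77%, in order to demonstrate that the lower 95% confidence interval of specificity is at least 70% or greater". The conclusion is "we would require 407 cases of negative or clinically insignificant prostate cancer", converted to 479 men for DEFINITION ONE and 543 for DEFINITION TWO.

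The conversions use the prevalences in section 9.2.1 (15% and 25%). Neither a sample size formula nor a confidence interval method is named. Section 9.2 then takes the largest requirement, 714 men, from the McNemar comparison in section 9.2.3 (107 cases).

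**The concern.** The stated aim is to rule out a sensitivity of 60% when the truth is 75%, and a specificity of 70% when the truth is 77%. The threshold is therefore the null value, and its variance belongs with the 2.5% tail. The expected value is the alternative, and its variance belongs with the 10% tail. The printed counts look as if these roles were exchanged. That calculation answers a different question: how many men are needed to reject 75% when the truth is 60%.

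The figures belong to the two primary outcomes. They do not set the sample size now, but they could. Section 9.2.4 promises a review of all the sample size assumptions, with an eye to limiting how many men have the combined biopsy. It also says that positive dependence between TRUS and MP-MRI may be more realistic than independence, and under positive dependence the McNemar requirement falls. Section 7.1 mentions dropping TRUS as one option that could be considered at a high sepsis rate, which would remove the McNemar requirement. In either case the sensitivity figure becomes the largest requirement for DEFINITION ONE.

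**Working it through.** **Inputs.** Two-sided 5% and 90% power (section 9.2.2), so z = 1.96 and 1.2816. Sensitivity: threshold p0 = 0.60, expected p1 = 0.75. Specificity: p0 = 0.70, p1 = 0.77. Prevalence 15% (DEFINITION ONE) and 25% (DEFINITION TWO), from section 9.2.1.

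**Reproducing the printed counts.** With the expected value on the 1.96 term,

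n = [1.96·√(p1(1−p1)) + 1.2816·√(p0(1−p0))]² / (p1−p0)²

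- Sensitivity: (1.96 × 0.4330 + 1.2816 × 0.4899)² / 0.15² = 96.89, rounded up to 97.
- Specificity: (1.96 × 0.4208 + 1.2816 × 0.4583)² / 0.07² = 406.94 (unrounded inputs), rounded up to 407.

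The totals follow: 97/0.15 = 646.7 → 647; 97/0.25 = 388; 407/0.85 = 478.8 → 479; 407/0.75 = 542.7 → 543. All six printed figures are reproduced.

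**Alternatives that do not reproduce them** (sensitivity / specificity):
- variance at the expected value in both terms: 87.6 / 379.8
- variance at the threshold in both terms: 112.1 / 450.3
- one-sided 5%: 82.3 / 341.2
- arcsine: 101.2 / 416.0
- continuity-corrected: 108.6 / 435.9
- logit: 116.6 / 455.2

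**Ordinary order for the stated aim.** With the threshold on the 1.96 term,

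n = [1.96·√(p0(1−p0)) + 1.2816·√(p1(1−p1))]² / (p1−p0)²

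- Sensitivity: 102.02 → 103 cases. 103/0.15 = 686.7 → 687 men; 103/0.25 = 412 men.
- Specificity: 421.71 → 422 non-cases. 422/0.85 = 496.5 → 497 men; 422/0.75 = 562.7 → 563 men.

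**Power.** By the same formula, power = Φ{[(p1−p0)√n − 1.96·√(p0(1−p0))] / √(p1(1−p1))}. The exact columns give the binomial probability that the lower 95% limit reaches the threshold.

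| Target | n | Formula | Clopper-Pearson | Wilson | Wald |
|---|---|---|---|---|---|
| Sensitivity, printed | 97 | 88.4% | 84.1% | 88.9% | 88.9% |
| Sensitivity, ordinary order | 103 | 90.3% | 90.3% | 90.3% | 90.3% |
| Sensitivity, at 714 men | 107 | 91.4% | 89.9% | 89.9% | 93.2% |
| Specificity, printed | 407 | 88.9% | 87.7% | 87.7% | 89.9% |
| Specificity, ordinary order | 422 | 90.0% | 88.6% | 90.6% | 90.6% |
| Specificity, at 714 men | 607 | 97.5% | 97.1% | 97.1% | 97.7% |

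The counts at 714 men are 714 × 0.15 = 107.1 and 714 × 0.85 = 606.9.

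**When the sensitivity figure would bind.** In Appendix V, Table A1, the two rows with more agreement than independence need 441 and 321 men for DEFINITION ONE. Both are below 647 and 687. Against 714, the printed figure suggests 714 − 647 = 67 men in hand; the ordinary order leaves 714 − 687 = 27.

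**The case against.** The other side has four good arguments.

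1. **The exchange is inferred.** No formula is printed. This stands as a caveat, but two separate parameter pairs match to the unit and none of the variants listed above does.

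2. **103 and 422 are not the only defensible counts.** The target is a confidence limit and no interval method is named. A Wald planning formula needs only 88 and 380. Exact power that stays at or above 90% needs 101 and 412 with a Wald limit, 108 and 433 with Wilson, and 112 and 445 with Clopper-Pearson. At 422 the Clopper-Pearson power is still 88.6%. This stands: 103 and 422 are the result of one standard formula and should be presented as such.

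3. **The loss is small.** By formula it is 1.6 points at 97 and 1.1 points at 407. A reader might take 84% as the true power for sensitivity, but that is a low point of the saw-tooth for one interval method; at n = 98 Clopper-Pearson gives 87.7%. Averaged over n ± 5, Wald power is 90.3% around 97 and 90.4% around 407, and Wilson power 88.0% and 88.7%. This also stands.

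4. **Nothing changes today.** The study recruits to 714 and replaces men who exit, and 714 exceeds every restated total. A reader might infer that the trial is underpowered for its primary outcomes, or that 714 leaves almost no reserve for sensitivity. The documents support neither as a general statement: power at 107 cases runs from 89.9% to 93.2% depending on the interval. No passage says recruitment will fall to 647, and any change in N would follow an independent review.

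The objection does not remove the mismatch itself. The printed counts do not follow from the stated aim in the usual way, and a review that relaxed the McNemar assumption would start from them.

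**Conclusion.** The point holds as a correction to stated figures. Under the one-sample normal-approximation formula applied in the direction of the stated aim, section 9.2.2 should give 103 cases rather than 97 (6 more, 6.2%) and 422 non-cases rather than 407 (15 more, 3.7%). For DEFINITION ONE that is 40 more men for the sensitivity requirement and 18 more for specificity. The printed counts carry about 88% and 89% power by that formula.

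The planned N of 714 is unaffected, provided the 15% prevalence holds. The correction matters only if 714 is reduced, when 647 would be taken as the floor for sensitivity under DEFINITION ONE although the same formula gives 687. The conclusion rests on the protocol's own prevalences and expected accuracies, and on the inference about which formula was used.

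**What to change.** In section 9.2.2, restate the requirements as 103 cases (687 men for DEFINITION ONE, 412 for DEFINITION TWO) and 422 non-cases (497 and 563 men). Name the sample size formula and the confidence interval method, and present the counts as the result of that formula. Add a sentence that 714 men still cover both, with about 90–93% power for sensitivity and 97–98% for specificity, depending on the interval method.

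In the sample size review under section 9.2.4, and in any assessment of a design without TRUS under section 7.1, use 687 rather than 647 as the DEFINITION ONE sensitivity requirement.

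The cost is six numbers and a few sentences. Recruitment, procedures and the planned N stay as they are.

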#### 9.2.3 MP-MRI versus TRUS

We have assumed TRUS detects 48% of clinically significant prostate cancer   and MP-MRI will detect at least 70% (conservative). Using McNemar's test for paired binary observations,  in order to show an absolute increase in the proportion of clinically significant cancers detected of at least 22% (from 48% to 70%) with a power of 90% and a 2-sided alpha of 5%, a total of 107 cases are required. This is equivalent to a total study population of **714** men for DEFINITION ONE, **428** men for DEFINITION TWO.

#### 9.2.4 Varying sample size assumptions

It is acknowledged that varying any of sample size assumptions could lead to either a decrease or increase in the required sample size. For illustrative purposes, the effect on the sample size for different assumptions is provided in Appendix V. The McNemar's test assumes that the results of TRUS and MP-MRI are independent. It is perhaps more realistic to assume that cancers detected by TRUS are more likely to be detected by MP-MRI than those missed by TRUS (and vice versa). Taking an example, where there is extremely high agreement between the two methods, and MP-MRI detects almost all cases diagnosed by TRUS (and some additional cancers), then approximately 320 and 192 men are required according to DEFINITION ONE and DEFINITION TWO (See Table A1, Appendix V). Therefore, we consider a total of 714 to be the maximum number of patients required to have all 3 tests (MP-MRI, TPM and TRUS biopsy) for this study. This study has been designed to have as short a time as practical between visits for patients and to minimise drop-out (withdrawal or loss to follow-up). Drop-out is expected to be low. If patients do exit the study after registration, or between the MP-MRI and CPB procedures, then further patients will be recruited so that the target number of patients having all 3 tests is maintained.

An independent review of all the sample size assumptions will be made following completion of the pilot study and during the course of the main trial. This will ensure that the optimum sample size is achieved to answer the objectives of this protocol. This will be done without compromising the integrity of the study while minimising the number of men undergoing the combined prostate biopsy procedure.

#### 9.3 Analysis plan

Full details of all analyses to be performed will be detailed in the Statistical Analysis Plan (SAP) and reporting of results will following the STARD (STAndards for the Reporting of Diagnostic accuracy studies) practice.

#### 9.3.1 Pilot study

#### Safety

The pilot study data will provide an estimate of the rate of sepsis (requiring hospitalisation) following the CPB procedure with ongoing monitoring for safety (as detailed in section 7.1).

#### **Recruitment rate**

The pilot study will also inform recruitment rate for the main study. The pilot is expected to recruit 50 patients from two centres over one year (which translates to approximately two men per centre per month). The main phase aims to recruit up to 714 men to have MP-MRI and the CPB procedure over an additional 2 to 3 years (approximately two to five men per centre per month).

The internal pilot data will also contribute to the main analyses and the recruitment rate should adequately account for start-up time across centres.

#### Preliminary cost-effectiveness modelling

A preliminary economic model based on existing sources of evidence will be developed. This will allow assessment of the key uncertainties in the cost-effectiveness of the new diagnostic pathway. This will inform the design of the main phase. See Section 10 for more details.

#### 9.3.2 Primary analysis of the main study

The primary analysis will be based on all evaluable data, excluding men without all three test results and any data rejected as part of the external MP-MRI QC/QA process (see section 6.6.1).

The sensitivities, specificities and predictive values will be calculated for MP-MRI based on the overall cancer score for MP-MRI and DEFINITION ONE for clinically significant cancer on TPM biopsy. Results will be presented in a 2 by 2 table (as shown below in Table 4) and estimates will be presented together with 95% confidence intervals (CI).

Table 4: 2 by 2 tables to	demonstrate accuracy of MP-MRI	with respect to TPM

		MP-MRI		
		+ve	-ve	Total
TPM	+ve	а	b	a+b
	- ve	С	d	c+d
	Total	a+c	b+d	

**Specificity** = d / (c+d) where, d = number of men testing negative on MP-MRI and negative for clinically significant cancer on TPM, c = number of men testing positive on MP-MRI who do not have clinically significant cancer on TPM.

**Negative Predictive Value (NPV)** = d / (b+d) where, d = number of men testing negative on MP-MRI and negative for clinically significant cancer on TPM, b= number of men testing negative on MP-MRI who have clinically significant cancer on TPM.

**Sensitivity** = a / (a+b) where, a = number of men testing positive on MP-MRI and positive for clinically significant on TPM, b = number of men testing negative for MP-MRI who have clinically significant cancer on TPM.

**Positive Predictive Value (PPV)** = a / (a+c) where, a = number of men testing positive on MP-MRI and positive for clinically significant on TPM, c = number of men testing positive on MP-MRI who do not have clinically significant cancer on TPM.

**Comparison of TRUS guided biopsy and MP-MRI**: McNemar's test will be used to compare the agreement between MP-MRI and TRUS biopsies in the subset of men found to have clinically significant prostate cancer according to DEFINITION ONE. Results will be presented in a 2 by 2 table as shown below in Table 5.

		MP-MRI		
		+ve	-ve	Total
TRUS	+ve	r	S	r+s
	- ve	t	u	t+u
	Total	r+t	s+u	Npairs

Table 5: 2 by 2 table demonstrating the comparison of TRUS guided biopsy and MP-MRI

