#### 6.2 Visit 3: Combined Prostate Biopsy (TPM + TRUS)

TPM will be performed first under the same general/spinal anaesthetic as the TRUS guided biopsy. The biopsy procedure is combined to reduce patient burden (two visits, two procedures) and also to minimise drop out of patients between biopsies. Biopsies will be taken every 5mm throughout the prostate using a template grid placed over the perineum. Biopsies will be oriented and individually identified to facilitate later correlation of results with imaging.

TRUS guided biopsy of the prostate is to be performed after TPM, under the same general/spinal anaesthetic. This helps ensure results are obtained for the reference test in a biopsy naïve gland that has not undergone swelling and distortion to allow better post-study comparisons of the TPM and MRI findings. It also minimises the risk of infection.

The surgeon performing the CPB procedure will be blind to the MRI results. TRUS guided biopsies will be done in the left lateral position. 10-12 core biopsies will be taken as per national guidelines. Each core will be identified and potted separately. The TPM and TRUS biopsy sets from a particular patient will be sent to different pathologists to minimise bias. The pathologists will independently report results to the MRC CTU on the separate TPM and TRUS electronic CRFs. Please refer to the PROMIS Combined Biopsy SOP.

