#### 6.10 Withdrawal

In consenting to the study, patients are consenting to study monitoring, imaging and biopsy procedures, followup, data collection and analysis. Patients are allowed to withdraw consent at any stage, however this is expected to be a very rare occurrence. Withdrawal may be complete (i.e. from further study procedures and any follow up), or partial (e.g. from study procedures but allowing the possibility of further follow up). All communication surrounding the withdrawal should be noted in the patient's records, and where withdrawal is complete no further PROMIS CRFs should be completed for that patient. Data up to the time of withdrawal can be included in the study if anonymised.

The MRC CTU should be informed of any patient withdrawals by sending in a completed Withdrawal Form. Patients registered into PROMIS but for whom there is no subsequent MP-MRI result or will not go on to have one or more of the study procedures should be withdrawn from the study and any remaining procedures.

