## 7. SAFETY REPORTING

#### 7.1 Safety monitoring during the pilot study

During the pilot study, the rate of sepsis following the CPB procedure will be prospectively recorded. Between 1% and 4% of patients undergoing TRUS guided biopsy alone develop sepsis requiring hospital admission, while the sepsis rate for TPM alone is <0.5%. This is because unlike the TRUS biopsy, TPM it is not administered via the transrectal route.

Although anticipated to be rare, each sepsis case will be reviewed by the TMG and where necessary by the Trial Steering Committee (TSC). Two sepsis cases out of the 50 patients in the pilot study would represent a sepsis rate of 4%. The TSC will review safety (sepsis, urinary retention) at completion of the internal pilot study, or sooner if 2 sepsis cases requiring hospitalisation are seen (and subsequently after a 2 further cases if necessary).

If the combination of TRUS and TPM leads to more than 2 cases of sepsis at any time (requiring hospital admission), there could be cause for concern and a requirement for modification of the study design. If deemed necessary for safety reasons, recruitment to the study will be suspended either during the pilot or the main phase of the study when ongoing safety monitoring would continue.

The TSC will make a recommendation regarding proceeding to the main phase which could include a modification to the study design. For example, if a sepsis rate of 10% (n=5) is observed the study remains viable but one of the following two options could be considered: (i) introducing an interval of 6 weeks between the TRUS biopsy and the TPM (which will likely lead to increased drop-out of patients) or (ii) dropping the TRUS biopsy from the study (which will prevent an analysis of the performance of TRUS biopsy but will not compromise the primary objective of the study). The TMG would seek independent recommendation from the TSC regarding these decisions.

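### Section 9.3.2 requires a TRUS result for MP-MRI accuracy figures that do not use TRUS, so complete MP-MRI/TPM pairs can be discarded, at a small cost in precision

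*Protocol*

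**What the plan says.** Section 9.3.2 opens with the rule for the whole primary analysis: "The primary analysis will be based on all evaluable data, excluding men without all three test results". It also removes scans rejected by the external MRI quality process, which is not at issue here.

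Two analyses then follow in the same section. Table 4 gives MP-MRI sensitivity, specificity, PPV and NPV against TPM under DEFINITION ONE; these are the measures behind both primary outcomes in section 9.1.1. Table 5 compares MP-MRI with TRUS by McNemar's test in TPM-positive men. Only Table 5 needs TRUS.

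On the order of procedures, section 6.2 states: "TRUS guided biopsy of the prostate is to be performed after TPM". Sections 6.2 and 6.8.2 send the two sets of cores to different pathologists, who report separately.

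On incomplete men, section 6.10 allows the following: "Data up to the time of withdrawal can be included in the study if anonymised". Section 9.2.4 covers replacement: "further patients will be recruited so that the target number of patients having all 3 tests is maintained".

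Section 7.1(ii) says that dropping TRUS after a high sepsis rate "will prevent an analysis of the performance of TRUS biopsy but will not compromise the primary objective of the study".

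**The concern.** The exclusion is tied to a test that plays no part in four of the primary estimates. Because TPM comes first and is read separately, TRUS can fail or go unreported after the reference result exists. Such a man has had the scan and the mapping biopsy under anaesthesia and fills a cell of Table 4, but is left out of it and replaced.

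What is at stake is information on sensitivity, the scarcer quantity because only 15% of men are expected to be cases. The rule also ties the recruitment target for MP-MRI accuracy to TRUS completion. That would matter if the sample size review foreseen in section 9.2.4 reduced the number needed for the TRUS comparison. The rule is written into the protocol, so it is not a detail left open for the SAP.

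**Working it through.** **Inputs from the protocol.** Prevalence under DEFINITION ONE is 15% (9.2.1). Sensitivity is taken as 75% against a lower limit of 60%, needing 97 cases and 647 men (9.2.2). MP-MRI 70% versus TRUS 48% needs 107 cases and 714 men (9.2.3). The discordant cells under independence are 0.364 and 0.144 (Appendix V, Table A1). Two-sided alpha is 5% and power 90%.

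**Input not in the protocol.** The share m of men who have MP-MRI and TPM but no TRUS result is assumed at 1%, 2% and 5%. Section 9.2.4 says only that drop-out should be low.

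**Step 1: reproduce the plan's figures.**
- McNemar: n = (1.96 × √0.508 + 1.2816 × √(0.508 − 0.22²))² / 0.22² = 106.07, so 107 cases. 107/0.15 = 713.3, so 714 men.
- Sensitivity: n = (1.96 × √(0.75 × 0.25) + 1.2816 × √(0.60 × 0.40))² / 0.15² = 96.9, so 97 cases. 97/0.15 = 646.7, so 647 men.

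Both agree. The 647 rests on MP-MRI and TPM alone; the 714 is the figure that needs TRUS.

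**Step 2: pairs left out when 714 three-test men are obtained.** Men with a pair = 714/(1 − m), rounded up. Pairs left out = that number minus 714. Cancers among them = pairs × 0.15. Half-width if all pairs are used = 1.96 × √(0.75 × 0.25 / (0.15 × n)).

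| Assumed m | Men with MP-MRI and TPM | Pairs left out | Cancers among them | Half-width using all pairs |
|---|---|---|---|---|
| 0% | 714 | 0 | 0 | 8.20 points |
| 1% | 722 | 8 | 1.2 | 8.16 points |
| 2% | 729 | 15 | 2.25 | 8.12 points |
| 5% | 752 | 38 | 5.7 | 7.99 points |

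Under the three-test rule the half-width stays at 8.20 throughout. At 5% the rule therefore costs 8.20 − 7.99 = 0.21 points. While 714 is the target, the TRUS comparison needs the replacement men anyway, so nobody extra is biopsied because of the rule.

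**Step 3: which target binds if the review lowers the TRUS requirement.** Table A1 gives 441 men (66 cases) or 321 men (48 cases) under closer agreement between the two tests. Either is below 647, so the sensitivity target would then bind. If only three-test men counted towards it, 647/(1 − m) gives 654 men at 1% and 682 at 5%, which is 7 to 35 more than 647. Counted separately, 647 biopsied men would be enough: at 5% missing TRUS, the 441 row needs 441/0.95, or 465 men.

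**The case against.** The strongest defence is that one common set is a legitimate choice in a paired cohort. Section 9.1.1 reports TRUS accuracy beside MP-MRI accuracy, and a single denominator keeps the figures comparable. TRUS is done under the same anaesthetic as TPM, drop-out is expected to be low and men are replaced. The one specific route to an incomplete set that the protocol describes, unblinding for advanced disease (6.8.3), usually omits TPM and keeps TRUS, so those men have no reference result under any rule.

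This stands as a limit on size. It does not justify the rule for Table 4, because the common set can be kept for every comparison that needs it.

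A reader might infer several stronger points that the protocol does not support.
- **That 7.1(ii) contradicts 9.3.2, or that dropping TRUS would lose the primary objective.** It is offered as a redesign on the Trial Steering Committee's recommendation, it discloses the loss of TRUS analysis, and both 9.1.1 outcomes remain measurable. Other three-test provisions would be amended at the same time.
- **That the six-week interval in 7.1(i) would discard many pairs.** Section 7.1 expects more drop-out, but gives no rate and does not fix which biopsy would come first. If TRUS came first, those who dropped out would lack TPM and the rule would cost nothing.
- **That 6.10 conflicts with 9.3.2, or should let a man who will not have TRUS go on to TPM.** The sentence on data up to withdrawal is permissive and does not define the primary set. At the 714 target, continuing such a man to TPM adds one more biopsied man who must still be replaced.
- **That the estimates are biased.** The protocol gives neither a rate nor reasons for missing TRUS, so only a loss of precision can be shown.

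**Conclusion.** The point holds as a minor inefficiency. Section 9.3.2 makes MP-MRI accuracy depend on a test it does not use, and valid reference-verified pairs can be lost. At an assumed 1% to 5% missing TRUS and 714 three-test men, the loss is about 8 to 38 pairs, of which 1 to 6 are cancers. At the top of that range the sensitivity half-width is 8.2 rather than 8.0 points. These figures rest on the assumed rates, 15% prevalence and 75% sensitivity.

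The 7 to 35 extra biopsied men arise only if the sample size review takes the TRUS requirement below 647. The protocol leans that way without committing to it: "It is perhaps more realistic to assume that cancers detected by TRUS are more likely to be detected by MP-MRI". The operative figure remains 714. The 7.1(ii) assurance about the primary objective holds once the 9.3.2 rule no longer requires TRUS for MP-MRI accuracy.

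**What to change.** 1. In 9.3.2, base MP-MRI sensitivity, specificity, PPV and NPV (Table 4) on all men with evaluable MP-MRI and TPM. Restrict the McNemar comparison (Table 5) and any TRUS figures shown beside MP-MRI to men with all three tests. Report MP-MRI accuracy in the three-test set as a sensitivity analysis.
2. In 9.2.4, state two targets and count them separately: 647 men with MP-MRI and TPM for accuracy, and 714 men with all three tests for the TRUS comparison under independence. The second can then be revised at the planned review without changing how the first is counted.

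Section 6.10 can stay as it is. The change needs no new data or procedures. Its cost is that two denominators have to be reported and explained; the paired comparison keeps a set common to both tests.
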